6.4.3 Response Assessment Dates

At each response assessment time point, scans to evaluate target and non-target lesions can be performed on multiple dates. If the time point response is CR or PR, then the latest date of all radiologic scans at the given response assessment visit will be the date of response. If the time point response is SD, then the earliest date of all radiologic scans at the given response assessment visit will be the date of SD. If the time point response is PD, then the earliest date that PD has been documented will be the date of PD, i.e. the earliest of:

- Date of target lesion assessments when the target lesion response is PD
- Date of non-target lesion assessments when the lesion status is unequivocal progression
- Date of documenting new lesions

For subjects whose best overall response is a confirmed CR or PR, the date of objective response will be the date of initial documentation of response (i.e., CR or PR that is subsequently confirmed).

6.4.4 Adequate Response Assessment

An adequate tumor assessment must include a radiologic scan with the overall disease response of CR, PR, SD, or PD.

6.4.5 Action Taken with Study Treatment of Adverse Events

Action taken with study treatment of each adverse event (AE) will be mapped to the Clinical Data Interchange Standards Consortium (CDISC) controlled terminology as listed below:

1. dose not changed
2. dose reduced
3. drug interrupted
4. drug withdrawn

Drug interruption includes dose elimination, dose delay, infusion interruption with full dose received, and infusion stop early without full dose received, as collected on the case report form (CRF). If more than one action is associated to an AE, the action taken that is the end result will be selected.

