Continue at same dose level.	Continue at same dose level. For Grade 2 thrombocytopenia, withhold dose until toxicity is \leq Grade 1 or has returned to baseline, then resume treatment at the same dose level or consider dose reduction by 1 dose level. Transfusions or growth factors may be used as indicated per institutional guidelines.	Withhold dose until toxicity is \leq Grade 1 or has returned to baseline, then resume treatment at the same dose level or consider dose reduction by 1 dose level. Transfusions or growth factors may be used as indicated per institutional guidelines.	Withhold dose until toxicity is \leq Grade 1 or has returned to baseline, then reduce dose by 1 dose level and resume treatment, or discontinue at the discretion of the investigator. Transfusions or growth factors may be used as indicated per institutional guidelines. For anemia, treatment discontinuation should be strongly considered.

Table 2: Recommended dose modifications for enfortumab vedotin-associated nonhematologic toxicity

Any Grade	Grade 1	Grade 2	Grade 3	Grade 4

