7.6.1 Adverse Events

Adverse events (AEs) will be summarized by MedDRA preferred term (PT) in descending frequency of occurrence unless otherwise specified. For incidence reporting, if a subject reports more than one AE that was coded to the same system organ class (SOC) or PT, the subject will be counted only once for that specific SOC or PT.

A treatment-emergent adverse event (TEAE) is defined as a newly occurring or worsening AE after the first dose of study treatment. See [Appendix B](#) for details regarding treatment-emergent classification.

An overall summary of TEAEs will be provided. Summaries of TEAEs by MedDRA classification will also be provided for the following:

- TEAEs
- Grade 3 or higher TEAEs
- Serious TEAEs
- TEAEs leading to dose interruption
- TEAEs leading to dose reduction
- TEAEs leading to treatment discontinuation
- TEAEs leading to death
- Treatment-related TEAEs
- Treatment-related grade 3 or higher TEAEs
- Treatment-related serious TEAEs
- Treatment-related TEAEs leading to dose interruption
- Treatment-related TEAEs leading to dose reduction
- Treatment-related TEAEs leading to treatment discontinuation
- Treatment-related TEAEs leading to death
- TEAEs by SOC, PT and maximum severity. At each SOC or PT, multiple occurrences of events within a subject are counted only once at the highest severity

- TEAEs by SOC and PT

All TEAEs, grade 3 or higher TEAEs, serious TEAEs, TEAEs leading to treatment discontinuation, and TEAEs leading to death will be listed.

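### The end-result rule for action taken leaves multi-action AEs out of the dose-interruption and dose-reduction tables, an undercount of unknown size

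*SAP*

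**What the plan says.** SAP 6.4.5 sets the derivation: "Action taken with study treatment of each adverse event (AE) will be mapped to the Clinical Data Interchange Standards Consortium (CDISC) controlled terminology". There are four possible values: dose not changed, reduced, interrupted and withdrawn. Interruption is defined broadly: "Drug interruption includes dose elimination, dose delay, infusion interruption with full dose received, and infusion stop early without full dose received". Where several actions apply, the rule is "If more than one action is associated to an AE, the action taken that is the end result will be selected".

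SAP 7.6.1 lists "TEAEs leading to dose interruption", "TEAEs leading to dose reduction" and "TEAEs leading to treatment discontinuation" as separate summaries. Each is repeated for related events, for example "Treatment-related TEAEs leading to dose interruption".

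Protocol 5.2.3, Table 1, tells the investigator to hold the drug for Grade 4 hematologic toxicity, "then reduce dose by 1 dose level and resume treatment, or discontinue at the discretion of the investigator". Table 2 calls for a hold on suspicion of SJS or TEN and permanent discontinuation once either is confirmed. At Grade 3, and for some Grade 2 events, the tables call for a hold followed by resumption at the same dose or, optionally, one level lower.

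**The concern.** The table titles in SAP 7.6.1 describe what an AE led to. The variable in SAP 6.4.5 describes how the AE ended. These agree only when an AE has one action. When a hold is followed by a reduction or withdrawal, the AE did lead to an interruption, but the retained value says otherwise and the interruption table loses it.

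Safety and tolerability is a secondary objective (SAP 2.2). A reader of the study report would take the interruption table as the count of AEs for which dosing was held. Under the rule it is the count of AEs for which a hold was the last step. The planned tables give the reader no way to see the difference.

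**Working it through.** The documents state no figure on this point, so there is none to reproduce. The check traces each sequence of actions through the rule to the tables, assuming first that all actions are attached to one AE record.

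| Actions on one AE record | Where the protocol provides for it | Value kept | Counted under | Missing from |
|---|---|---|---|---|
| Hold, resume at same dose | Tables 1 and 2, Grade 3; some Grade 2 events | interrupted | interruption | none |
| Hold, then reduce | Table 1, Grade 4; optional at Grade 3 and for some Grade 2 events | reduced | reduction | interruption |
| Hold, then withdraw | Table 1, Grade 4; Table 2, suspected then confirmed SJS/TEN | withdrawn | discontinuation | interruption |
| Reduce, later withdraw | Possible, not a listed path | withdrawn | discontinuation | reduction |
| Immediate withdrawal | Table 2, most Grade 4 events and Grade 3 or 4 pneumonitis/ILD; Protocol 5.4.1, anaphylaxis | withdrawn | discontinuation | none |

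**Direction.** Let A be the set of AEs with any interruption recorded, and E the set whose end result is interruption. E is contained in A, so count(E) ≤ count(A). Equality holds only if no interrupted AE ends with a different action. The same holds for reductions. The rule can remove AEs from these two tables and cannot add any. Withdrawal is by nature the last action, so the discontinuation table should not lose events this way.

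**Link between the two sections.** SAP 7.6.1 does not name the variable behind its tables. SAP 6.4.5 is the only action-taken derivation in the SAP, and nothing elsewhere retains the earlier action.

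**From AE to subject.** SAP 7.6.1 counts a subject once per preferred term. A subject is lost from a row of the interruption table only if every interrupted record under that term ended in another action.

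**Unit of the rule.** The SAP does not say whether an AE here means one record or one condition. In SAP Appendix A, Example 1, a single identifier for headache carries six dated records with changing severity. SAP Appendix B links such records by identifier. If the hold is entered on one record and the reduction on the next, both actions survive. If both are on one record, the hold is lost.

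**Size.** The number missing depends on three quantities that the documents do not give: the share of reductions and withdrawals preceded by a hold for the same AE, the share of those with both actions on one record, and the share of affected subjects with no other interrupted record under that term.

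**The case against.** The best defence has four parts.

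First, the convention is stated openly, and no AE vanishes from the safety reporting: a superseded hold shows up as a reduction or a withdrawal. For a dose held and never resumed, reporting a withdrawal alone is defensible. This stands as far as it goes, but it does not make the interruption table count what its title says.

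Second, other summaries soften the effect. SAP 7.4 and Protocol 9.3.9.1 summarize dose modifications, and SAP 7.6.1.1 pools dose modifications for AEs of special interest. Tables by grade and seriousness are untouched. This also stands, but none of these restores interruption counts by preferred term across all AEs.

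Third, the protocol path is narrower than a reader might infer. Tables 1 and 2 are recommendations. A hold that is expected to lead to a further step is firm only for Grade 4 hematologic toxicity and confirmed SJS/TEN; at Grade 3 the reduction is optional. This stands. It also rules out saying that the loss falls on the most severe events: most Grade 4 nonhematologic events, Grade 3 pneumonitis/ILD and anaphylaxis go directly to discontinuation, so they have no recommended hold to lose.

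Fourth, a reader might try to size the loss from the phase 1 figures at 1.25 mg/kg in Protocol 1.6: 16/97 = 16.5% reduced and 13/97 = 13.4% withdrawn for AEs, together 29/97 = 29.9%. The documents do not support that as an estimate or a bound for this trial. It needs every reduction and every withdrawal to follow a hold for the same AE, no overlap between the two groups, no other interrupted record, and phase 1 rates carried over to this study. Halving it to about 15% only replaces one unsupported share with another.

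**Conclusion.** The concern holds for AE records with more than one action. Applied as written, SAP 6.4.5 leaves hold-then-reduce and hold-then-withdraw records out of the interruption tables, and reduce-then-withdraw records out of the reduction tables, both overall and treatment-related. The error runs one way, toward low counts.

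The conclusion assumes that the SAP 7.6.1 tables use the SAP 6.4.5 variable, and that at least some sequences are recorded on a single AE record. The first is a fair reading, since no other derivation is given. The second is implied by the rule itself, which would be unnecessary if an AE never carried several actions.

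The size is unknown. At subject level it could be small if records are split by severity or if subjects have other interrupted records under the same term. The matter is confined to descriptive safety tables in a single-arm study; the ORR, DOR, PFS and OS analyses are unaffected. It merits correction because the remedy is cheap and the tables would otherwise be misread.

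**What to change.** In SAP 6.4.5, derive three separate flags for each AE (interrupted, reduced, withdrawn) from all actions recorded on the CRF. Say whether the unit is a record or a condition, and link records by the AE identifier already used in Appendix B. In SAP 7.6.1, build each table from any action of the relevant type. Keep the single end-result value only as the controlled-terminology variable, and state how end result is ordered.

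State also whether a hold that turns into a withdrawal without resumption counts in both tables. A footnote saying that only the final action is counted would prevent misreading but would not supply the missing counts.

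The cost is a change of SAP wording and a small programming change. SAP 6.4.5 indicates that the CRF collects the component actions, so no new data collection should be needed; the CRF itself is not among the documents, so this should be confirmed. The reported interruption and reduction rates can rise, and the categories will no longer be mutually exclusive, which the table footnotes should say.

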6.5 Handling of Dropouts and Missing Data

Missing data will not be imputed unless otherwise specified.

For time-to-event endpoints (e.g., duration of response, PFS, and OS), subjects who have no specified event will be censored as specified for each respective endpoint in Section 7.5.

Subjects who do not have at least two (initial response and confirmation scan) post-baseline response assessments will be counted as non-responders for the analysis of primary endpoint.

Missing AE dates will be imputed for the purpose of calculating duration of events and treatment-emergent status (see [Appendix A](#) for imputation details and [Appendix B](#) for treatment-emergent definition).

Missing prior therapy dates will be imputed for the purpose of calculating the time from prior therapy to first dose of study drug (see [Appendix C](#) for details).

Missing subsequent anticancer therapy start date will be imputed for the purpose of deriving the time-to-event endpoints as applicable (see [Appendix D](#) for details).

Unless otherwise specified, if the numeric value of a laboratory test is not available because it is below the lower limit of quantification (LLOQ), the result will be analyzed as equal to the LLOQ when a numeric value is required (e.g., calculating the mean) and be listed as “< LLOQ” in the listings.

6.6 Multicenter Studies

There are multiple centers in this study, however it is not anticipated that any center will accrue enough subjects to warrant an analysis by center.

6.7 Multiple Comparison/Multiplicity

No multiple comparisons are planned and no alpha adjustment is needed because only one primary endpoint will be tested in this single-arm study.

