9.3.1.5 Multiple Comparisons and Multiplicity

No multiple comparisons are planned and no alpha adjustment is needed because only one primary endpoint will be tested in this single arm study.

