9.3.1.9 Timing of Analyses

The primary analysis on Cohort 1 (platinum-treated patients) will be conducted when enrollment is completed in Cohort 1, and all patients in the cohort have been followed for at least 6 months, or have discontinued from study, or had 30 days safety follow-up after PD, whichever comes first. Analysis for Cohort 2 will occur at 4 timepoints: 1) at the time of analysis of Cohort 1, 2) when approximately 50 patients in Cohort 2 have had the opportunity to be followed for approximately 8 months from the first dose of enfortumab vedotin, 3) when approximately 70 patients in Cohort 2 have had the opportunity to be followed for approximately 8 months from the first dose of enfortumab vedotin, and 4) when all patients

in Cohort 2 have had the opportunity to be followed for approximately 8 months from the first dose of enfortumab vedotin. All patients may also be analyzed at the time of analysis of Cohort 1 and/or Cohort 2.

Additional cutoff dates may be defined and corresponding database locks may occur to allow for more precise estimates of time-to-event endpoints.

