9.3.10 Interim Analyses

An IDMC will periodically monitor the trial for safety. The IDMC will review expedited SAEs as they are received. Further details will be provided in the IDMC Charter.

In addition, an ongoing real-time review of SAEs will be conducted by Seagen Pharmacovigilance.

Additionally, available data for Cohort 2 will be summarized at the time of the primary analysis of Cohort 1 (e.g., the estimated ORR and its 2-sided 95% exact Clopper-Pearson CI), after approximately 50 patients in Cohort 2 have had the opportunity to be followed for approximately 8 months from the first dose of enfortumab vedotin, and after approximately 70 patients in Cohort 2 have had the opportunity to be followed for approximately 8 months from the first dose of enfortumab vedotin. All patients may also be analyzed at the time of analysis of Cohort 1 and/or Cohort 2.

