6.2 Determination of Sample Size

The study is designed to estimate the confirmed ORR in the full analysis set and to detect an improvement in the ORR compared with a historical 10% response rate.

The primary efficacy hypothesis is

$$H_0: ORR \leq 10\% \text{ vs. } H_a: ORR > 10\%$$

Approximately 200 subjects will be enrolled to ensure collection of sufficient efficacy and safety data, including approximately 100 or more platinum-treated subjects (Cohort 1) and up to approximately 100 platinum-naïve and cisplatin-ineligible subjects (Cohort 2). Using the estimate of approximately 100 subjects in Cohort 1, the study will have 98% power to detect a 15% increase in ORR from 10% to 25%, and 81% power to detect a 10% increase in ORR from 10% to 20%, at one-sided significance level of 0.025, based on exact methods using EAST®, Version 6.0, by Cytel Inc.

The confirmed ORR and 95% exact CI for subjects in Cohort 2 will be summarized at 4 timepoints:

- 1) at the time of the primary analysis of Cohort 1 (i.e., after all subjects in Cohort 1 have had the opportunity to be followed for at least 6 months),
- 2) when approximately 50 subjects in Cohort 2 have had the opportunity to be followed for approximately 8 months from the first dose of enfortumab vedotin,
- 3) when approximately 70 subjects in Cohort 2 have had the opportunity to be followed for approximately 8 months from the first dose of enfortumab vedotin, and
- 4) when all subjects in Cohort 2 have had the opportunity to be followed for approximately 8 months from the first dose of enfortumab vedotin.

For illustration purpose, assuming the observed ORR in Cohort 2 is 30%, the 95% exact CIs of ORR based on the expected number of subjects at each analysis timepoint are summarized below:

Number of Subjects	95% Exact CI
N=20	(12%, 54%)
N=50	(18%, 45%)
N=70	(20%, 42%)
N=100	(21%, 40%)

Sample Size for IDMC Assessment of Slit Lamp Examination

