7.5.1 Primary Efficacy Endpoint - Objective Response Rate (ORR) per IRF

The primary endpoint of this study is the confirmed ORR per IRF. ORR is defined as the proportion of subjects whose best overall response is a confirmed CR or PR according to RECIST v1.1 (Eisenhauer 2009). Subjects who do not have at least two (initial response and confirmation scan) post-baseline response assessment will be considered non-responders.

The primary efficacy hypothesis is outlined in Section 6.2.

The ORR per IRF and its exact two-sided 95% CI will be calculated for the full analysis set.

In addition, the ORR per IRF will be summarized and presented graphically by the subgroups defined in Section 6.8.

The maximum percent reduction from baseline in the sum of diameters per IRF will be calculated for each subject and presented graphically with a waterfall plot.

Time to response per IRF will be calculated as the time from the first dose of study drug to the first documentation of objective response (CR or PR that is subsequently confirmed).

Time to response per IRF will be summarized for the responders only. Subgroup analysis of time to response will be performed for subjects who responded to the prior CPI therapy versus those who did not respond to the prior CPI therapy.

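### Does an ORR hypothesis that names no cohort, with four Cohort 2 analyses and no alpha adjustment, leave the type I error uncontrolled?

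*SAP*

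**What the plan says.** SAP 6.2 opens the hypothesis with "The primary efficacy hypothesis is" and sets ORR at most 10% against ORR above 10%. No cohort or analysis time is given beside it. SAP 7.5.1 adds nothing further: "The primary efficacy hypothesis is outlined in Section 6.2".

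The design figures in the same section belong to one cohort: "Using the estimate of approximately 100 subjects in Cohort 1, the study will have 98% power" for a rise from 10% to 25%, and 81% for a rise to 20%, by exact methods at one-sided 0.025. Cohort 2 is treated differently: "The confirmed ORR and 95% exact CI for subjects in Cohort 2 will be summarized at 4 timepoints", followed by a table of intervals that assumes an observed ORR of 30%.

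On timing, Protocol 9.3.1.9 says: "The primary analysis on Cohort 1 (platinum-treated patients) will be conducted when enrollment is completed in Cohort 1". No Cohort 2 analysis carries the label of primary analysis. Protocol 9.3.10 says that "available data for Cohort 2 will be summarized at the time of the primary analysis of Cohort 1", and again at about 50 and about 70 patients.

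On pooling, SAP 6.1 plans analyses by cohort and combined by default, while Protocol 9.3.1 and 9.3.5.1 make the combined analysis optional.

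On multiplicity, SAP 6.7 says: "No multiple comparisons are planned and no alpha adjustment is needed because only one primary endpoint will be tested in this single-arm study". Protocol 9.3.1.5 matches it: "no alpha adjustment is needed because only one primary endpoint will be tested in this single arm study".

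**The concern.** One endpoint is not the same as one test. The endpoint here could be compared with 10% in Cohort 1, in Cohort 2 on four occasions, and in the pooled patients. The reason given for not adjusting alpha speaks only to the number of endpoints. It is silent on populations, pooling and repeated analyses. Because the hypothesis in SAP 6.2 is not tied to a cohort, a reader could take a Cohort 2 or pooled lower bound above 10% as a rejection of the SAP's primary hypothesis. Someone else could take the same bound as an estimate. If every such bound counted as a success, the chance of at least one false claim would be well above the nominal one-sided 0.025.

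**Working it through.** **Inputs.** Null ORR 10%, one-sided 0.025, exact method, about 100 Cohort 1 subjects, alternatives 25% and 20% (SAP 6.2, Protocol 9.1). Cohort 2 sizes of 20, 50, 70 and 100 are the documents' own illustration (same sections).

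**Step 1: reproduce the plan's figures.** The smallest r with P(X ≥ r | n=100, p=0.10) ≤ 0.025 is r = 17, with probability 0.0206. This matches the interval: the Clopper-Pearson 95% lower bound is 10.2% for 17/100 and 9.4% for 16/100.

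- Power at 25%: P(X ≥ 17 | 100, 0.25) = 0.979, stated as 98%.
- Power at 20%: P(X ≥ 17 | 100, 0.20) = 0.808, stated as 81%.
- Cohort 2 intervals at 30% observed: 6/20 gives 11.9–54.3%, 15/50 gives 17.9–44.6%, 21/70 gives 19.6–42.1%, 30/100 gives 21.2–40.0%. All agree with the printed table.

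**Step 2: see which cohort each element of a test belongs to.**

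| Element | Cohort 1 | Cohort 2 | Pooled |
|---|---|---|---|
| Analysis named as primary | yes (Protocol 9.3.1.9, SAP 6.10) | no | no |
| Stated power and one-sided level | yes (SAP 6.2, Protocol 9.1) | no | no |
| Verb used for ORR in the sample-size section | detect | summarize, all four timepoints | not mentioned |
| Success or stopping rule | none beyond the test | none | none |

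The fourth Cohort 2 timepoint is missing from Protocol 9.3.10, but that section covers interim analyses and would not list a final one. SAP 6.2 and Protocol 9.1 include it among the four summaries.

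**Step 3: error under the ordinary reading.** One test in Cohort 1 at one analysis gives 0.0206, below 0.025. Nothing needs adjusting.

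**Step 4: error if the 10% rule were applied elsewhere (hypothetical).** True ORR is 10% and all responses are taken as mature.

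- Each cohort tested once at N=100: 1 − (1 − 0.0206)² = 0.0408 for at least one false positive. Each cohort's own error stays at 0.0206.
- A claim at any Cohort 2 look, sizes 20/50/70/100, thresholds 6/10/13/17 responders. The probabilities of first crossing are 0.0113 + 0.0199 + 0.0084 + 0.0085 = 0.0481.
- Look sizes are approximate. A first look at 10 or 30 instead of 20 gives 0.0514 or 0.0443. Assumed sizes of 20/60/80/100, allowing for extra recently treated patients, give 0.0373.
- Cohort 1 or any Cohort 2 look at 20/50/70/100: 1 − (1 − 0.0206)(1 − 0.0481) = 0.0677.

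Every figure in this step needs a test that the current text does not specify.

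**The case for a change.** The best case on the other side is that Cohort 1 only is an inference, and some text points away from it. SAP 6.2 refers to ORR in the full analysis set, which holds both cohorts. The primary objective covers both populations. Protocol 3.2 supports the 10% benchmark for platinum-treated and for cisplatin-ineligible patients, and treats a lower bound that excludes 10% as meaningful at about 100 patients, a size that Cohort 2 may also reach. Protocol 9.3.5.1 gives estimates and intervals for each cohort and no test, while Protocol 9.3.1.5 still speaks of one endpoint being tested.

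Part of this stands. The hypothesis has no cohort beside it, and the one-endpoint reason does not explain the conclusion it supports. But the multiplicity sentence also says that no multiple comparisons are planned, which fits one test plus estimation. A benchmark used to interpret an interval is not a decision rule, and no consequence follows from a Cohort 2 interval at any look.

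The joint figures (0.0408 and 0.0677) also presuppose that error should be controlled across both cohorts. They are distinct populations analysed separately, and statisticians would differ on whether two such questions share one error budget.

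**Conclusion.** The wording gap is real, but no change to the plan follows. Carried out as written, the plan gives one sound exact test in Cohort 1 (error 0.0206 at N=100; power 97.9% and 80.8% against the stated 98% and 81%), with exact 95% intervals for Cohort 2 and any pooled analysis. The conclusion that no alpha adjustment is needed is right on that reading; only the explanation is incomplete. A sentence naming the cohort would record what the power statement, the timing section and the Cohort 2 summaries already imply. It would alter no estimate, interval, sample size or decision.

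This rests on two assumptions: that the hypothesis belongs to the Cohort 1 primary analysis, and that Cohort 2 and pooled lower bounds are reported as estimates. If a Cohort 2 lower bound above 10% were claimed as a success at whichever look it first appeared, the second assumption would fail and the one-sided error would be about 0.048 at 20/50/70/100. That would be a fault in the reporting, since the plan provides for no such claim.
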